2.1.4.2.12 Estimated Parasite Reduction Ratio Parameters

After calculating the parasite clearance rate, the parasite reduction ratios (PRR) will be calculated in log10 unit as:

- PRR24 = clearance rate constant [1/hours]*24 hours/ln(10)
- PRR48 = clearance rate constant [1/hours]*48 hours/ln(10)
- PRR72 = clearance rate constant [1/hours]*72 hours/ln(10)

2.1.4.3 *Exploratory efficacy endpoints*

- Time to clearance of gametocytes on blood smear for patients with gametocytes at baseline.
- Time to appearance of gametocytes on blood smear for patients with no gametocytes at baseline.
- Detection of Pfs25 mRNA by RT-PCR, in order to assess the impact of IP on levels of mature gametocytes up to the asexual parasite clearance, but also later, to check the absence of pernicious effects on gametocytemia and transmission. Time to clearance of gametocytes by RT-PCR for patients with no gametocytes at baseline, and time to appearance of gametocytes by RT-PCR for patients with no gametocytes at baseline will be estimated but may be reported outside of the CSR. (See Section 2.4.4.4).
- Parasitemia determined by blood thick films and by qPCR to evaluate the relationship between parasitemia and concentration of OZ/FQ, at all parasitemia time-points. The relationship between parasitemia by qPCR and concentration of OZ/FQ, if performed will be reported separately.

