4 OBJECTIVES AND ENDPOINTS

Table 1 - Objectives and endpoints

Objectives	Endpoints
Primary	
To show the contribution of OZ439 to the clinical and parasiticidal effect of OZ439/FQ combination by analyzing exposure-response of OZ439 measure by Day 28 PCR-corrected ACPR for the effect and the AUC of OZ439 as PK predictor	Section 10.3.1.1 for details)
Secondary	
• To evaluate the dose response of OZ4 combined with FQ on PCR-corrected	• Day 28 PCR-corrected ACPR (see Section 10.3.1.1 for details)
and crude Day 28 ACPR	 Day 28 crude ACPR (see Section 10.3.1.1 for details)
 To evaluate the dose-response of OZ4 combined with FQ on selected secondary endpoints 	• Parasitemia (/µl) at baseline then every 6 h during the first 36 h then at 48 h and every 24 h until Day 7
	• observed PRR at 24 h, 48 h, and 72 h
	• time (h) to 99% parasite reduction
	• time (h) to parasite clearance
	 Parasite clearance rate
	• time (h) to recrudescence or re-infection
	 time (h) elapsed below LOQ of parasitemia
• To evaluate the safety and tolerability different dosages of OZ439 in	• AEs including SAEs, AESIs and TEAEs
combination with FQ and FQ alone	 Clinical laboratory tests (including LFT), vital signs, and ECG including QTc assessment
	• Physical examination and clinical signs and symptoms related to uncomplicated P. falciparum malaria (fever, dizziness, headache, nausea, anorexia, vomiting, diarrhea, itching, urticaria, skin rash,

Objectives	Endpoints
	abdominal pain, joint pain, muscle pain, palpitations, sleep problems, confusion, hearing problems, vision problems, and fatigue).
 To characterize the PK of OZ439 in plasma, and of FQ and its active metabolite SSR97213 in blood 	 Concentrations of OZ439 in plasma, and of FQ and SSR97213 in blood at specific time points
	 PK parameters for OZ439 in plasma, and for FQ and SSR97213 in blood, including:
	- C _{max}
	- t _{max}
	- C _{168h}
	- AUC
	$ t_{1/2}$
	• AUC _{0-Day 28} for FQ and SSR97213 only
Tertiary/exploratory	· · · · ·
To explore the impact of study treatment on functional gametocytemia	• Quantitative reverse transcription Polymerase Chain Reaction (RT-qPCR) to measure gametocyte maturation stage (expression of Pfs 25 mRNA)
To evaluate the relationship between parasitemia and concentration of OZ439/FQ	• Quantitative Polymerase Chain Reaction (qPCR) and RT-qPCR to explore, at all parasitemia time-points, the PK/PD of OZ439/FQ (to be reported in a separate report).

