1.2.3 Tertiary/exploratory objectives

The exploratory objectives of this study are:

- To explore the impact of study treatment on functional gametocytemia
- To evaluate the relationship between parasitemia and concentration of OZ439/FQ
- To evaluate the relationship between QTc and concentration of OZ439/FQ

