2.1.4.2.3 Parasite clearance time (PCT)

For a conservative approach, parasite clearance should not be claimed based on negative parasitemia obtained by imputation. Therefore, in this section **no imputation of missing parasitemia** will be used, except in case of concomitant fever where the missing parasitemia will be considered as positive.

Timing to consider

In this section, except otherwise specified, the post-dose timing associated to a parasitemia will refer to:

- its assigned time point as defined in [Section 2.5.4.1](#), if it exists,
- its actual post-dose timing as defined in [Section 2.5.4](#) and expressed in hours, if outside defined time windows. None or very few are expected, otherwise it should be taken into account in the analyses.

Establishing the clearance

A blood thick film is considered negative when asexual forms of *P. falciparum* are reported as absent on the dedicated e-CRF page, even if other species are reported.

The parasite clearance will be concluded as soon as two consecutive thick films are negative, with second film prepared within 6 to 12 hours of the first (actual times). In case, the second film has been performed less than 6 hours or greater than 12 hours of the first, then the parasite clearance will be confirmed or invalidated by the thick film following the second one, whatever the timing of this third film:

- If this third film is negative, then the clearance is confirmed.
- If this third film is positive, then the clearance is invalidated.

Time to parasite clearance

When the parasite clearance is confirmed, the time to parasite clearance is the post-dose timing associated to the first negative thick film, as defined above.

In case the parasite clearance is not observed or confirmed before withdrawn (for any reason) or before start of rescue therapy, then the time to parasite clearance will be censored at the time of the last blood film (using the post-dose timing above defined) before withdrawn or rescue therapy start, whichever comes first. Blood films (including date and time of recording) performed the day of rescue start are regarded as before rescue.

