2.4.4.4 Additional efficacy analyses

Additional efficacy analyses will be reported and analysed in the mITT population.

- Disease characteristics post-baseline

Descriptive statistic of the number (%) of patients experiencing clinical signs or symptoms related to malaria will be provided at each visit and for each sign or symptom, regardless of the presence of the sign/symptom at baseline, and within the subset of patients who the sign/symptom at baseline.

- Time to gametocytes clearance (blood smears)

Time to gametocytes clearance will be analyzed using Kaplan-Meier estimators. An overall overview including number of events and cumulative incidence of events with 95% CI will be provided in a summary table, survival curves will be plotted.

- Time to appearance of gametocytes (blood smears)

The first appearance of gametocytes will be presented by time after enrollment for all patients, by treatment arm. The denominator for computation of percentages is the mITT population within each treatment arm. Besides, time to gametocytes clearance will be analyzed using Kaplan-Meier estimators in the same way than time to gametocytes clearance.

- Time to gametocytes clearance (RT-qPCR)

Time to gametocytes clearance will be analyzed using Kaplan-Meier estimators. An overall overview including number of events and cumulative incidence of events with 95% CI will be provided in a summary table, survival curves will be plotted.

- Time to appearance of gametocytes (RT-qPCR)

The first appearance of gametocytes will be presented by time after enrollment for all patients, by treatment arm. The denominator for computation of percentages is the mITT population within each treatment arm. Besides, time to gametocytes clearance will be analyzed using Kaplan-Meier estimators in the same way than time to gametocytes clearance

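### SAP 2.1.4.3 defines RT-PCR gametocyte clearance in patients with nothing to clear, and the appearance analysis in SAP 2.4.4.4 does not match its own endpoint definition (minor, exploratory)

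*SAP*

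**What the plan says.** The objective is exploratory: "To explore the impact of study treatment on functional gametocytemia" (SAP 1.2.3). Protocol Section 4, Table 1, ties it to RT-qPCR of Pfs25 mRNA, used "to measure gametocyte maturation stage".

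SAP 2.1.4.3 defines four time-to-event gametocyte endpoints. The smear clearance endpoint reads "Time to clearance of gametocytes on blood smear for patients with gametocytes at baseline", and smear appearance is restricted to patients without gametocytes at baseline. For RT-PCR, clearance reads "Time to clearance of gametocytes by RT-PCR for patients with no gametocytes at baseline" and appearance reads "time to appearance of gametocytes by RT-PCR for patients with no gametocytes at baseline". The two RT-PCR endpoints therefore share one patient set.

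SAP 2.4.4.4 describes the analyses. For appearance, by smear and again by RT-qPCR, it presents the results for all patients and adds: "The denominator for computation of percentages is the mITT population within each treatment arm". Under each of those two headings it continues: "Besides, time to gametocytes clearance will be analyzed using Kaplan-Meier estimators in the same way than time to gametocytes clearance".

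**The concern.** A time-to-clearance analysis needs patients who carry gametocytes at time zero, and a time-to-appearance analysis needs patients who do not. The SAP breaks the first rule for RT-PCR clearance. For appearance it contradicts itself between the definition (2.1.4.3) and the analysis (2.4.4.4).

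The clearance error falls on the assay that the protocol names for this objective. In a patient negative at baseline, a program that takes the first negative sample as clearance would record the event at the first post-dose sample, whatever the treatment. The appearance percentage would depend on how many patients carried gametocytes at baseline as well as on treatment. Time to appearance, read literally, would get no survival analysis. The study is open label, so risk sets and denominators are better fixed in the text than settled after data have been seen.

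**Working it through.** The documents give no gametocyte rate, sample size or power, so there is no planned figure to reproduce. The check is a comparison of the text, followed by arithmetic on the denominator.

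**Step 1: the definitions against the analyses.**

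| Endpoint | Patients in SAP 2.1.4.3 | Patients who can have the event | SAP 2.4.4.4 |
|---|---|---|---|
| Smear clearance | Gametocytes at baseline | Same: correct | Kaplan-Meier; no restriction stated |
| Smear appearance | None at baseline | Same: correct | All patients, mITT denominator; Kaplan-Meier sentence names clearance |
| RT-PCR clearance | None at baseline | Gametocytes at baseline: **opposite** | Kaplan-Meier; no restriction stated |
| RT-PCR appearance | None at baseline | Same: correct | All patients, mITT denominator; Kaplan-Meier sentence names clearance |

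Three of the four definitions are right. The RT-qPCR clearance paragraph in 2.4.4.4 states no baseline restriction, so it does not repair the fourth.

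**Step 2: effect of the mITT denominator on appearance.**

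Inputs:
- n = 30 evaluable patients per arm (Protocol 5.2).
- g, the baseline carriage, is not given; assumed 5% to 30%.
- r, the true appearance rate among baseline-negative patients, is not given; assumed 20% for illustration.

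Formulas:
- Patients at risk of appearance per arm: 30(1 − g). Baseline carriers per arm: 30g.
- Percentage over the mITT if carriers count as non-events: r(1 − g).
- Percentage over the mITT if presenting all patients lets carriers count as having appeared: r(1 − g) + g.
- SD of the chance difference in carriage between two arms: √(2g(1 − g)/30).

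| g | At risk | Carriers | Carriers as non-events | Carriers as appeared | SD of carriage difference |
|---|---|---|---|---|---|
| 5% | 28.5 | 1.5 | 19% | 24% | 5.6 points |
| 10% | 27 | 3 | 18% | 28% | 7.7 points |
| 20% | 24 | 6 | 16% | 36% | 10.3 points |
| 30% | 21 | 9 | 14% | 44% | 11.8 points |

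With the baseline-negative denominator every row would show 20%. Under the first reading the relative understatement equals g whatever r is. Under the second, r = 10% would be reported as 14.5% (g = 5%) to 37% (g = 30%).

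**Step 3: effect on a comparison of arms.** Take two arms with the same r = 20% but carriage of 10% and 30%. They would show 18% and 14% under the first reading, a gap of 4 points or 1.2 patients in 30. Under the second they would show 28% and 44%, a gap of 16 points or 4.8 patients. A 20-point difference in carriage is 20/10.3 = 1.9 SD at g = 20%, so it is an unfavourable case and not the typical one. A 10-point difference, about one SD, would separate the arms by 0.20 × 10 = 2 points or 0.80 × 10 = 8 points.

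**Step 4: the Kaplan-Meier sentence.** Under both appearance headings it says that clearance is analysed in the same way as clearance. Clearance already has its own paragraph for each assay. No sentence in 2.4.4.4 specifies a Kaplan-Meier analysis of appearance.

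**The case against.** The best reply is that these are drafting slips. The RT-PCR clearance phrase repeats the wording of the appearance clause beside it, the smear endpoint has the right set, and the Kaplan-Meier sentence refers to itself, so the intention can be guessed. That is probably true, and it lowers the severity. It does not remove the need to correct rules that would be programmed as written.

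A second reply is that no gametocytes at baseline could mean smear-negative patients whose submicroscopic carriage is found by RT-qPCR, which Protocol 9.1.1.5 says the assay is meant to detect. The wording allows this, but the SAP names no baseline assay for either RT-PCR endpoint. That reading also needs to be stated.

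A third reply is that a percentage over the mITT is a legitimate, if diluted, summary. It would be, if the SAP said how carriers are counted and did not define the endpoint in a different set.

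Two stronger inferences are tempting, and the documents do not support them. One is that the gametocyte objective cannot be answered. Three definitions are sound, and detection of Pfs25 mRNA, the protocol's own endpoint, is kept in 2.1.4.3 and run at all scheduled time points.

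The other is that all four endpoints must be censored at rescue, because for asexual clearance the SAP says "or before start of rescue therapy, then the time to parasite clearance will be censored" and the gametocyte sections are silent. The silence is real. But no document says that the rescue drugs act on gametocytes, and the choice of drug is left to the investigator. Rescue is triggered largely by treatment failure, so censoring there may be informative and is a debatable choice of estimand. The 28% and 3% failure figures implied by the planning rates (100 − 72 and 100 − 97) are simulated PCR-corrected failures in the FQ-alone and 1000 mg arms. They are not rescue rates.

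**Conclusion.** The SAP is wrong as written in three places: the patient set for RT-PCR clearance, the patients and denominator for appearance by both assays, and the Kaplan-Meier sentence under both appearance headings. The first and third are textual facts and need no assumption, apart from the unstated baseline assay.

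The size of the second depends on carriage and appearance rates that the documents do not give. At r = 20% and g from 10% to 30%, the reported percentage runs from 18% down to 14% or from 28% up to 44%, depending on how carriers are counted. The direction of the error is therefore not established, and neither understatement nor overstatement should be claimed alone.

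The point is minor. The objective is exploratory, no hypothesis or power is attached to it, the RT-PCR times may be reported outside the clinical study report, and the primary and secondary analyses are untouched.

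**What to change.** Four wording changes to the SAP:

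1. In 2.1.4.3, define time to RT-PCR clearance in patients positive for gametocytes by RT-qPCR at baseline.
2. In 2.1.4.3, state that baseline gametocyte status is judged by the same assay as the endpoint: smear for smear, RT-qPCR for RT-qPCR.
3. In 2.4.4.4, for both assays, take the numerator, denominator and risk set for appearance from mITT patients negative at baseline by that assay, and report their number per arm.
4. In 2.4.4.4, under both appearance headings, change the Kaplan-Meier sentence so that time to appearance of gametocytes is what is analysed.

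The cost is SAP text and the matching table and program specifications. No data collection, sample size or primary analysis changes. The corrected clearance set will be small, 30 × 5% = 1.5 to 30 × 30% = 9 patients per arm over the assumed range, so its estimates should be presented as descriptive.

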2.1.5 Safety endpoints

The safety analysis will be based on the reported adverse events (AEs) and other safety information, such as clinical laboratory data, liver function tests, vital signs, ECG (centrally read, triplicate), and physical examination.

Observation period

For all safety data, the observation period will be divided into three segments:

- The **pre-treatment period** is defined as the time from the signed informed consent date up to the start time of first IMP administration (excluded)
- The **on-treatment period** is defined as the time from the start of the first dose of study drug administration up to the Day 28 visit.
- The **post-treatment period** is defined as the time after Day 28 visit (excluded)

The on-study observation period is defined as the time from start of treatment until the end of the study, i.e., last protocol planned visit or the resolution/stabilization of all SAEs.

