7.7.1 Rescue medicine

The study site will supply rescue medication that will be obtained locally upon local recommendation.

The use of established anti-malarial drug combination per WHO recommendations (6) and per local regulations and the choice of the best therapeutic option is left at investigator's decision.

The use of rescue medications is allowed as soon as

- vomiting occurs during FQ dosing or after FQ dosing but before OZ439 administration,
- vomiting occurs within 35 minutes after OZ439 re-dosing (see Section 7.1.1.2), or
- there is evidence of treatment failure (see definition below).

If no rescue medication is administered before Day 28, it will be administered on Day 28.

Treatment failure is defined according to WHO recommendations (2) as follows:

Early treatment failure (one the following)

- danger signs or severe malaria on Day 1, 2, or 3 in the presence of parasitemia;
- parasite count on Day 2 higher than on Day 0, irrespective of axillary temperature;
- parasitemia on Day 3 with axillary temperature ≥ 37.5 °C;
- parasite count on Day $3 \ge 25\%$ on Day 0.

Late clinical failure

- danger signs or severe malaria on any day between Day 4 and Day 28 in the presence of parasitemia, without previously meeting any of the criteria of early treatment failure;
- presence of parasitemia and axillary temperature ≥37.5°C (or history of fever) on any day between Day 4 and Day 28, without previously meeting any of the criteria of early treatment failure.

Late parasitological failure

• presence of parasitemia on any day between Day 7 and Day 28 and axillary temperature <37.5°C, without previously meeting any of the criteria of early treatment failure or late clinical failure.

Before giving a rescue therapy before Day 28, where possible:

- a PK (OZ439 and FQ) sample should be taken
- blood films, parasite genotyping, RT-qPCR, and qPCR must be taken

Following administration of rescue therapy before Day 28, patients should be managed according to local standard of care practices. Safety data, parasitemia (blood films), and PK data should continue to be collected in the e-CRF, according to the study schedule, and up to the end of the study (Day 28) even if re-emergence is confirmed.

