10.3.2.1 Observation period

For all safety data (see Section 9.2 and Section 9.4 for details), the observation period will be divided into three phases:

- The pre-treatment phase defined as the time between the participant gives informed consent and the start time of first IMP administration (excluded)
- The on-treatment phase defined as the start time of first dose of IMP administration (included) up to Day 28 visit (included)
- The post-treatment phase will be defined as the time after the Day 28 visit (excluded)

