The “hypothetical” logistic regression model (eq 2, see below) used for simulations was a composite of the “PQP/OZ-ACPR28 model” built by MMV, modeling PCR-corrected ACPR at Day 28 probability (p) as a function of OZ439 and PQP concentrations at Day 7 and baseline log₁₀-parasitemia, and of assumptions made on FQ efficacy, which were based on the results of part 1. Precisely, β_{FQ} was fixed at 0.12 by calibration to get ~ 72% success ACPR at Day 28 for FQ 400 mg alone for a baseline parasitemia greater than 3000 parasites/ μ L, and the following parameters were extracted from the MMV model: $\alpha=3.23$, $\beta_{OZ439}=0.73$, and $\beta_{BasePar}=-1.27$.

$$(eq\ 2)\ log(p/(1-p)) = \alpha + \beta_{FQ} \cdot \text{Conc}_{D7,FQ} + \beta_{OZ439} \cdot \text{Conc}_{D7,OZ} + \beta_{BasePar} \cdot \log_{10}(\text{BasePar})$$

Using all these assumptions, the PCR-corrected ACPR at Day 28 rates simulated in the 4 arms FQ 400 mg + OZ439 at 0, 300, 600 and 1000 mg were of 72%, 81%, 91%, and 97% for a baseline parasitemia greater than 3000 parasites/ μ L.

Clinical trials analyses

Exposure-effect analyses of the simulated clinical trials were performed, consisting of a logistic regression model of exposure at Day 7 for both drugs, with baseline parasitemia as covariate, and the Day 28 PCR-corrected ACPR as response variable (as in eq 2 above). Significance of OZ439 concentration effect (β OZ439) was analyzed using a 2-sided alpha Wald test at 5%.

Overall, five thousand trial simulations were performed, and the power was deduced as the percentage of significant simulated trials. Results estimated that 30 evaluable participants per treatment arm will yield a power around 90% to detect an OZ439 concentration effect relation (in a population of patients with a baseline parasitemia greater than 3000 parasites/ μ L, for 4 arms FQ 400 mg + OZ439 at 0, 300, 600, and 1000 mg).

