2.4.4.2.2 Parasitemia

Descriptive statistics (n, mean, geometric mean, standard deviation, median, Q1, Q3, minimum, and maximum) for parasitemia data (number of parasites/ μ L) (raw data and absolute change from baseline) will be displayed at baseline, and each post-baseline assessment.

Time profile plots (Mean \pm SEM) of parasitemia will be provided for each treatment arm, one curve per arm.

Box-Whisker plots over time of positive parasitemia levels will be provided by treatment arm.

Assessments performed after start of rescue treatment will not be included in above summaries

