2.4.5 Analyses of safety data

The summary of safety results will be presented by actual treatment group.

General common rules

All safety analyses will be performed on the safety population as defined in Section 2.3.3, unless otherwise specified, using the following common rules:

- Safety data in patients who do not belong to the safety population (eg, exposed but not randomized) will be listed separately.
- The potentially clinically significant abnormality (PCSA) values are defined as abnormal values considered medically important by the Sponsor according to predefined criteria/thresholds based on literature review and defined by the Sponsor for clinical laboratory tests, vital signs, and ECG.
- PCSA definitions (version dated May 2014) depending on the age, race, or sex of the patient are detailed separately in [Appendix A]. Specific PCSA criteria for children will use children's age at time of laboratory, vital signs and ECG assessments. Age will be collected in the eCRF by the clinical site.
- PCSA criteria will determine which patients had at least 1 PCSA during the on-treatment period, taking into account all evaluations performed during the on-treatment period, including nonscheduled or repeated evaluations. The number of all such patients will be the numerator for the on-treatment PCSA percentage.
- The treatment-emergent PCSA denominator by group for a given parameter will be based on the number of patients assessed for that given parameter in the on-treatment period by treatment group on the safety population.
- For quantitative safety parameters based on local laboratory/reading measurements, descriptive statistics will be used to summarize results and change from baseline values by visit and treatment group. Summaries will include the endpoint value and/or the worst on-treatment value. The endpoint value is commonly defined as the value collected at the same day/time of the last administration of IMP. If this value is missing, this endpoint value will be the closest value prior to the last dose intake. The worst value is defined as the nadir and /or the peak on-treatment post-baseline according to the direction (minimum or maximum) of the abnormality as defined in the PCSA list.
- Analyses of the safety variables will be essentially descriptive and no systematic testing between treatment groups is planned.

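### Pooled safety displays run through rescue therapy to Day 28 without separating post-rescue data, which can dilute an OZ439 dose-related safety signal

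*SAP*

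**What the plan says.** SAP 2.1.5 states that the on-treatment period "is defined as the time from the start of the first dose of study drug administration up to the Day 28 visit". Protocol 10.3.2.1 sets the same window and counts the Day 28 visit in it. Protocol 7.7.1 keeps data flowing after early rescue: "Safety data, parasitemia (blood films), and PK data should continue to be collected in the e-CRF, according to the study schedule", up to Day 28.

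Several safety displays then pool the whole window:

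- TEAEs are events that develop, worsen or become serious at any time in it (SAP 2.1.5.1), and the AESI tables count treatment-emergent events (2.4.5.1).
- PCSAs are derived "taking into account all evaluations performed during the on-treatment period, including nonscheduled or repeated evaluations" (SAP 2.4.5).
- Laboratory, vital-sign and ECG tables include a worst on-treatment value, and the e-DISH plot uses peak ALT and peak bilirubin (SAP 2.4.5.3 to 2.4.5.5).

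The efficacy side is handled differently. For parasitemia, SAP 2.4.4.2.2 says: "Assessments performed after start of rescue treatment will not be included in above summaries". SAP 2.1.4.2.3 censors time to parasite clearance at rescue if clearance has not been confirmed by then. No safety section has a matching rule or a supplementary display.

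The documents give no expected rescue rate. The nearest figures are the simulated PCR-corrected ACPR rates in SAP 1.3, which "were of 72%, 81%, 91%, and 97% for a baseline parasitemia greater than 3000 parasites" per microlitre, for OZ439 0, 300, 600 and 1000 mg.

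**The concern.** A secondary objective is the safety of different OZ439 doses with FQ against FQ alone. After early rescue, a patient has taken a second antimalarial regimen of the investigator's choice. Later adverse events and liver or blood values then reflect that regimen as well as the study drugs. If patients are rescued because treatment failed, and OZ439 prevents failure, post-rescue data collect in the FQ-alone and low-dose arms. A true rise in events or ALT with OZ439 dose would then look flatter than it is, because OZ439 works. Hepatic effect is an identified risk of both components (Protocol 3.3), and laboratory tests at Days 7, 14, 21 and 28 overlap the period when late failures occur.

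**Working it through.** **Plan's own figures.** Inflating 30 evaluable per arm for 15% dropout gives 30/0.85 = 35.3, against the stated 35 per arm and 140 in total. A simulation of the plan's second equation, calibrated to the stated response rates, gave 89% to 93% power against the stated figure of around 90%. Exposure variability is not given, so CVs of 40–50% (FQ) and 50–100% (OZ439) were assumed. The response rates themselves are taken as stated.

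**Failure by arm** (1 − ACPR, with 35 per arm):

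| OZ439 dose | ACPR | Failure | Patients |
|---|---|---|---|
| 0 mg | 72% | 28% | 9.8 |
| 300 mg | 81% | 19% | 6.7 |
| 600 mg | 91% | 9% | 3.2 |
| 1000 mg | 97% | 3% | 1.1 |

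**From failure to rescue.** Rescue is triggered by failure before PCR correction, so re-infection counts. It is also triggered by vomiting, including after OZ439 re-dosing, which cannot happen with FQ alone. With s the ACPR, ρ an assumed re-infection risk equal in all arms and v an assumed re-dose vomiting rescue in the top arm only, rescue is 1 − s(1 − ρ) for FQ alone and 1 − s(1 − ρ)(1 − v) for 1000 mg. This treats every failure as rescued early.

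| Assumed ρ, v | FQ alone | 1000 mg | Ratio | Difference (points) |
|---|---|---|---|---|
| 0, 0 | 28.0% | 3.0% | 9.3 | 25.0 |
| 2%, 0 | 29.4% | 4.9% | 6.0 | 24.5 |
| 5%, 0 | 31.6% | 7.9% | 4.0 | 23.8 |
| 10%, 0 | 35.2% | 12.7% | 2.8 | 22.5 |
| 20%, 0 | 42.4% | 22.4% | 1.9 | 20.0 |
| 0, 5% | 28.0% | 7.9% | 3.6 | 20.2 |
| 5%, 5% | 31.6% | 12.5% | 2.5 | 19.1 |

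The ratio is unstable, but the difference, which drives the dilution, stays near 20 to 25 points. The direction reverses only if 0.97(1 − v) < 0.72, that is, v above 1 − 0.72/0.97 = 26%.

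**Size of the dilution.** Let b be the event risk without rescue, f the fraction rescued before Day 28 and r the event risk after rescue. Observed incidence is b + (1 − b)·f·r. The documents give neither b nor r. Assume b = 5% and r = 30%:

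- FQ alone: 0.05 + 0.95 × 0.28 × 0.30 = 13.0%
- 1000 mg: 0.05 + 0.95 × 0.03 × 0.30 = 5.9%
- Gap with no true difference: 0.95 × 0.25 × 0.30 = 7.1 points

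Varying the inputs:

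- r = 10% or 50%: 2.4 or 11.9 points.
- Re-infection 5%, 10% or 20%: 6.8, 6.4 or 5.7 points.
- 5% vomiting rescue in the top arm: 5.7 points, or 5.5 with 5% re-infection as well.
- FQ-alone failure over the range implied by the SAP's 90% CI for its ACPR (16% to 43%), top arm held at 3%: 3.7 to 11.4 points.
- Only half of failures rescued before Day 28: 0.95 × 0.125 × 0.30 = 3.6 points.

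**Effect on a true signal.** Suppose true risks are 10% with FQ alone and 20% at 1000 mg, and rescue adds the event in 20% of rescued patients. The observed risks are 0.10 + 0.90 × 0.28 × 0.20 = 15.0% and 0.20 + 0.80 × 0.03 × 0.20 = 20.5%. A 10-point difference shrinks to 5.4. At 10% or 30% after rescue it shrinks to 7.7 or 3.2.

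**The case against.** A reader might take 28% against 3% to mean that rescue is expected about nine times more often with FQ alone. The documents do not support that. The figures are simulated PCR-corrected failure, which Protocol Appendix 8 itself calls approximate. Re-infection and vomiting rescue bring the ratio down, and vomiting rescue works in the opposite direction. Failures first found on Day 28 are treated when the window closes and add almost no post-rescue time.

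Other parts of the opposing case also stand:

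- By-visit laboratory, vital-sign and ECG summaries do not pool time. They are less affected, though their Day 14 to 28 rows still mix rescued and unrescued patients.
- Symptoms of uncomplicated malaria are not adverse events unless serious (Protocol 9.2.6), so recurrence itself adds few TEAEs.
- A reader might infer that QT findings are masked. Scheduled ECGs end at 168 h and the concentration/ECG model uses hours 2 to 48 (SAP 2.4.6.3), so only rescue before the 168 h ECG matters, and the model is largely spared.
- The post-rescue risk is an assumption. At 35 per arm, 7.1 points is about 2.5 patients, against a standard error of about 6.9 points for 13.0% versus 5.9%. Safety analyses are descriptive.
- Censoring at failure is informative and removes most follow-up from FQ alone, while study-drug effects may continue after rescue. Reporting everything to Day 28 is a legitimate main display.

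The SAP's tables of events related to FQ or OZ439 and its listing of possible Hy's law cases help only in part. Relatedness is judged open label, and the PCSA and worst-value displays have no such split.

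**Conclusion.** The gap is real and cheap to close. The safety window includes post-rescue time, no TEAE, AESI, PCSA, worst-value or e-DISH display separates it, and the plan's own response rates place more of it in the FQ-alone arm. Dilution of an OZ439 dose-related signal is plausible, mainly for adverse events and for pooled laboratory and liver displays covering Days 7 to 28.

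Its size cannot be fixed from the documents. At the plan's point rates, with an assumed 5% base risk and 30% post-rescue risk, about 7 points is the most that would be hidden, reached only if every failure is rescued before Day 28. It is about half that if half are. The direction holds over all the re-infection and vomiting rates tried.

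A reader might also conclude that the Day 28 tables are wrong, or that a pre-rescue analysis should replace them. Neither follows: the pre-rescue set has its own bias and can only be supportive.

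**What to change.** Keep the Day 28 summaries in SAP 2.1.5 and 2.4.5 as the main display, and add:

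- a flag on every adverse event and abnormality that starts after rescue therapy begins;
- supplementary TEAE, AESI, PCSA and liver summaries censored at the start of rescue, with person-days at risk per arm;
- a rule for events on the day of rescue. SAP 2.5.1 notes that medication dates carry no time. The SAP already treats blood films on that day as before rescue, and the same convention would serve;
- a statement that both sets are read together when OZ439 doses are compared with FQ alone, and that the censored set is supportive because its follow-up is informative and shorter in failing patients.

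The cost is SAP wording and one extra set of tables. Rescue dates are already collected, and no rescue rule or visit changes.
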